## **4.2 OTHER TREATMENTS, EMERGENCY PROCEDURES, RESTRICTIONS**

### **4.2.1 Restrictions**

#### **4.2.1.1 Restrictions regarding concomitant treatment**

SRD and MRD cohorts 1 & 2: As per judgement of the investigator, administration of local SoC treatment such as IVT or peribulbar injections, laser, or other surgical treatment is allowed in clinically significant worsening of the disease. After the end of treatment with trial medication (during Follow-up Period, starting at Visit 5), SoC therapy is at the discretion of the investigator. SoC therapy is, for the purpose of the present trial, considered a non-investigational medical treatment.

MRD cohort 3: For the study eye, no other treatment (IVT or otherwise) is allowed during the treatment and follow up periods of the trial unless rescue criteria are met (refer to [Section 5.2.2](#) for rescue treatment criteria), or as deemed medically appropriate during/after Visit 6. Medications listed under the exclusion criteria ([Section 3.3.3](#)) are restricted during the trial. SoC therapy is, for the purpose of the present trial, considered a non-investigational medical treatment.

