## 5.2.2 Time to recurrence

Time to recurrence will be assessed in the MRD part from last trial drug administration to occurrence of any of the following in the study eye, leading to the use of wAMD rescue medication as decided by the investigator:

- Increase in CFST  $\geq$  75  $\mu$ m with a decrease in BCVA of  $\geq$  5 letters compared to Visit 5,
- OR
- Decrease in BCVA of  $>$  5 letters compared to baseline (Visit 2), due to worsening wAMD activity,
- OR
- Decrease in BCVA of  $\geq$  10 letters compared to the best prior BCVA, due to worsening wAMD activity

The decision to treat with wAMD rescue medication should be documented in the eCRF.

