### Evaluable Responders' Set (ERS, MRD cohort 3 only)

The ERS will consist of all patients who completed three doses of BI 836880 and have SD-OCT measurements at Week 16 (Visit 6).

In the TSAP, the FAS and ERS definitions may be updated, and further analysis data sets may be defined.

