6.4 SUBJECT SETS ANALYSED

Enrolled set (ES):

This subject set includes all patients who were enrolled in the study regardless of whether they were treated or not. The ES is used for the disposition table / listing and the disclosure tables for enrolment.

Section 7.3 of the CTP:

Treated Set (TS)

The TS will consist of all patients who were treated with at least one dose of BI 836880.

Full Analysis Set (FAS; only MRD part)

The FAS will consist of all patients who were treated with at least one dose of BI 836880 and have baseline and on-treatment CSFT measurements for the study eye in the time interval from drug administration to week 12. It will be used for the analysis of CSFT (change and percent change) only.

Evaluable Responders' Set (ERS, MRD cohort 3 only):

The ERS will consist of all patients who completed three doses of BI 836880 and have SD-OCT measurements at Week 16 (Visit 6) and haven't received SoC or any prohibited medication through week 16.

Patients with iPDs related to efficacy assessments that are expected to majorly affect the validity of assessment of efficacy at week 16 will be excluded from ERS. These include for

e.g., lack of compliance (including missed treatments, treatment misallocation and treatment/OCT assessment outside window), missing data, SoC or any prohibited medication, improper assessment at reading center and deviation from inclusion/exclusion criteria.

Any dropouts or withdrawals prior to completion of three doses of BI 836880 will be considered as a criterion of exclusion from ERS. In addition, any dropouts or withdrawals after completion of three doses of BI 836880 will also be excluded from ERS, unless SD-OCT measurements are available for that patient at Week 16.

Pharmacokinetic parameter analysis set (PKS):

This set includes all subjects in the treated set (TS)

- who received at least one dose of the test product BI 836880 and
- who provide at least one PK endpoint that was not excluded due to a protocol deviation relevant to the evaluation of PK or due to PK non-evaluability. Thus, a subject will be included in the PKS, even if he contributes only one PK parameter value for one period to the statistical assessment.

Descriptive and model-based analyses of PK parameters will be based on the PKS.

Table 6.4: 1 Subject sets analyzed

| Class of endpoint | ES | TS | FAS | ERS | PKS |
|---|----|----|-----|-----|-----|
| Primary endpoints | | X | | | |

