| Analysis of CSFT (percent) change from baseline – MRD part only | | | X | | |
| Other secondary and further endpoints | | X | | | |
| Responder analysis | | | | X | |
| Safety parameter | | X | | | |
| Demographic/baseline parameter | | X | | | |
| Important protocol deviations | | X | | | |
| Disposition/Disclosure (enrolment) | X | | | | |
| PK, ADA and PD analysis | | | | | X |

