The data format for descriptive statistics of concentrations will be identical with the data format of the respective concentrations. The descriptive statistics of pharmacokinetic parameters will be calculated using the individual values with the number of decimal places as provided by the evaluation program. Then the individual values as well as the descriptive statistics will be reported with three significant digits in the CTR.

Tabulations of frequencies for categorical data will include all possible categories available in the CRF and will display the number of observations in a category, as well as the percentage (%) for each dose group. Percentages will be rounded to one decimal place and will be based on all patients in the respective subject set whether they have non-missing values or not. The category 'missing' will be displayed only if there are missing values.

Units of variables should be given in the titles or column/row descriptors in round brackets (e.g. (mg)).

Exclusion of PK parameters

The ADS ADPP (PK parameters) contains column variables APEX and APEXCO indicating inclusion/exclusion (APEX) of a PK parameter and an analysis flag comment (APEXCO). All analyses based on the PKS will include parameters if they are not flagged for exclusion that is APEX is equal to "Included".

Exclusion of PK concentrations

The ADS ADPC (PK concentrations per time-point or per time-interval) contains column variables ACEX or ACEXCO indicating inclusion/exclusion (ACEX) of a concentration and an analysis flag comment (ACEXCO). Exclusion of a concentration depends on the analysis flag comment ACEXCO. For example, if ACEXCO is set to 'ALL CALC', the value will be excluded for all types of analyses based on concentrations. If ACEXCO is set to 'DESC STATS', the value will be excluded from descriptive evaluations per planned time point/time interval. If ACEXCO contains the addition 'TIME VIOLATION' or 'TIME DEVIATION', the value can be used for further analyses based on actual times. If ACEXCO is set to 'HALF LIFE', the value will be excluded from half-life calculation (and, consequently, any calculation that relies on λz) only; the value is included for all other analyses.

Further details are given in 001-MCS-36-472 "Noncompartmental Pharmacokinetic / Pharmacodynamic Analyses of Clinical Studies" (5) and 001-MCS-36-472_RD-03 "Description of Analytical Transfer Files and PK/PD Data Files" (9).

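### SAP Table 6.4: 1 puts the cohort 3 Week 16 responder analysis on the ERS only, and the ERS drops patients given SoC for worsening; an all-treated rate should stand beside it

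*SAP*

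**What the plan says.** SAP Table 6.4: 1 has columns for the ES, TS, FAS, ERS and PKS, in that order. The responder row reads "Responder analysis | | | | X", so its only mark is under the ERS. The row for comparable endpoints reads "Other secondary and further endpoints | | X", which is a mark under the TS.

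Protocol 7.3 defines the set by two conditions: "The ERS will consist of all patients who completed three doses of BI 836880 and have SD-OCT measurements at Week 16". It adds that "In the TSAP, the FAS and ERS definitions may be updated". SAP 6.4 uses that permission and adds a third condition: the patient must not have "received SoC or any prohibited medication through week 16". It also removes patients with important protocol deviations expected to have a major effect on the Week 16 efficacy assessment.

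SAP section 7 says that percentages "will be based on all patients in the respective subject set whether they have non-missing values or not".

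For the study eye in cohort 3, protocol 4.2.1.1 says that "no other treatment (IVT or otherwise) is allowed during the treatment and follow up periods of the trial unless rescue criteria are met", or as judged medically appropriate from Visit 6 (Week 16) onwards. The criteria in protocol 5.2.2 are a loss of BCVA, or a rise in CSFT together with a loss of BCVA, "leading to the use of wAMD rescue medication as decided by the investigator".

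The amendment 7 log (protocol 11.7) records that protocol 7.3.3 lets the responder analysis use the TS, the ERS or both. Protocol 7.3.3 itself and SAP 7.6.1 are not visible.

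**The concern.** Before Visit 6, a cohort 3 patient can be given permitted SoC in the study eye only after meeting criteria for worsening. That patient then fails the SAP's ERS condition and is absent from both the numerator and the denominator of the responder rate. No visible rule counts the patient as a failure, and SAP 6.3 on intercurrent events is marked not applicable. The rate is therefore computed in a set selected on a post-treatment event related to outcome.

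Protocol 1.4 calls these patients the intended final target population, and the cohort has only about 12 of them, so each exclusion moves the percentage visibly. SAP section 4 also says that the separate endpoints on absence of fluid and resolution of SHRM/PED could be removed. The ERS rate might then be the only visible summary of Week 16 resolution.

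Two wording gaps add to this:

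- The SoC condition names neither the eye nor whether SoC given after the Week 16 OCT counts, although SoC is allowed at Visit 6 itself.
- SAP 6.4 names eligibility deviations among those that can exclude a patient from the ERS. Code A1 in SAP Table 6.2: 1 says that such deviations exclude from no analysis set.

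**Working it through.** The documents give no responder rate, no number removed and no target rate for cohort 3, so there is no figure to reproduce. What follows is an illustration.

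**Inputs**

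- N = 12 treated. Protocol 7.7 plans approximately 12.
- r = responders among those kept in the ERS. Assumed 4, with 6 as a second case.
- k = treated patients removed from the ERS. Assumed 1 to 4.
- m = number of the k removed who count as responders at Week 16. Assumed 0 to k.

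**Formulas**

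- ERS rate = r/(N − k)
- All-treated rate = (r + m)/N

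**Step 1: every removed patient is a non-responder (m = 0)**

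| k | ERS, r = 4 | All treated | Difference (points) | ERS, r = 6 | All treated | Difference (points) |
|---|---|---|---|---|---|---|
| 1 | 4/11 = 36.4% | 33.3% | +3.0 | 6/11 = 54.5% | 50.0% | +4.5 |
| 2 | 4/10 = 40.0% | 33.3% | +6.7 | 6/10 = 60.0% | 50.0% | +10.0 |
| 3 | 4/9 = 44.4% | 33.3% | +11.1 | 6/9 = 66.7% | 50.0% | +16.7 |
| 4 | 4/8 = 50.0% | 33.3% | +16.7 | 6/8 = 75.0% | 50.0% | +25.0 |

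With k = 0 the two rates are equal.

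**Step 2: direction, with r = 4 and k = 2**

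- m = 0: 40.0% against 4/12 = 33.3%, difference +6.7
- m = 1: 40.0% against 5/12 = 41.7%, difference −1.7
- m = 2: 40.0% against 6/12 = 50.0%, difference −10.0

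In general r/(N − k) > (r + m)/N rearranges to rk > m(N − k), that is, m/k < r/(N − k). The ERS rate is too high only when the removed patients respond less often than those kept.

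**Step 3: who can be among the k**

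Rescue is only one route out. SAP Table 6.2: 1 also excludes from the ERS for an incorrect dose (C1), treatment out of window (C2), improper washout (D1), prohibited medication (D2) and OCT out of window (E2). SAP 6.4 adds eligibility and reading-centre problems. Such patients may well have responded. Two responders removed under C2, for example, give the m = 2 line above.

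A rescued patient is not a certain non-responder either. Rescue turns on BCVA, or on CSFT with BCVA. Response (SAP section 4) is clearance of both intraretinal and subretinal fluid, or of SHRM/PED. Someone rescued before Visit 6 could have a later OCT that shows resolution, and would count as a responder on the TS unless a rule says otherwise.

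**The case against.** The case for leaving the plan alone has real strength. A set free of SoC is a legitimate way to describe anatomical response without the effect of other treatment. The endpoint is descriptive, in an uncontrolled cohort of about 12, and no hypotheses are tested. Rescue medication is tabulated separately (SAP 7.2), recurrence curves by cohort use the TS (SAP 7.5.2), and individual values are listed (SAP 7), so a reader could build an all-treated count by hand. Counting rescue and missing OCTs as failures also makes a composite that differs from observed anatomical response.

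Most of this stands, and it is why the ERS rate should be kept. It does not remove the case for the second rate: those displays show the rescued patients, but the visible SAP states no all-treated responder rate.

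A reader might infer three stronger things that the documents do not support:

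- **The SAP breaches the protocol.** It does not. The ERS alone satisfies the wording recorded for 7.3.3, and protocol 7.3 lets the TSAP update the ERS. The update's absence from SAP section 4 is a record-keeping matter.
- **No all-treated analysis is planned.** This cannot be said while protocol 7.3.3 and SAP 7.6.1 are not visible. Only the table mark can be read.
- **The ERS rate must be inflated.** Step 2 of the working shows that it can also fall below the all-treated rate.

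**Conclusion.** The point holds in a limited form. On the visible text, the responder analysis is on the ERS only, and patients given SoC for worsening leave its denominator instead of counting as non-responders. This is selection on a post-treatment event in a descriptive further endpoint. It does not contradict the protocol and touches no primary or secondary endpoint.

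The size is unknown because neither the number removed nor the number of responders is given. With 12 treated and 4 responders kept, both assumed, removing 1 to 4 non-responders raises the rate by 3.0 to 16.7 points. If the two patients removed are both responders, the ERS rate is 10.0 points too low. The change is worth making because it is cheap and lets readers see both rates. Confidence is moderate, given the text that cannot be read.

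**What to change.** 1. In SAP Table 6.4: 1, mark the TS (cohort 3) as well as the ERS for the responder analysis. Beside the ERS rate, report responders over all treated cohort 3 patients.
2. For the all-treated rate, count as non-response: study-eye SoC before the OCT used for Week 16, fewer than three doses, or no Week 16 OCT. State that patients outside the ERS for any other reason (C1, C2, D1, D2 other than SoC, E2, eligibility or reading-centre issues) count by their observed Week 16 status.
3. Put this rule in SAP section 4 as part of the endpoint definition, because protocol 7.5 rules out imputing missing efficacy data. The SAP's denominator rule already keeps missing values in the percentage base, but it does not settle the status of a rescued patient whose later OCT shows resolution. List the ERS update in section 4 too, for the record.
4. State in SAP 6.4 whether the SoC exclusion means study-eye SoC before the Week 16 OCT.
5. Reconcile the eligibility-deviation exclusion in SAP 6.4 with code A1 in Table 6.2: 1.

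If text that is not visible already contains a TS responder analysis, align Table 6.4: 1 with it and add the non-response rule. Exact intervals are optional.

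The cost is one table mark, short wording in sections 4 and 6.4, one alignment with Table 6.2: 1 and one small extra table. The all-treated rate may come out lower or higher than the ERS rate. It is sure to be lower or equal only when every removed patient counts as non-response.

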Criteria for Pharmacokinetics	
Further criteria of interest:
 
SRD part:
 

Systemic pharmacokinetics of BI 836880 after a single intravitreal dose

Systemic immunogenic response (pre-existing anti-drug antibody [ADA], treatment emergent ADA)

 
MRD part:
 

Systemic exposure of BI 836880 after multiple intravitreal doses

Systemic immunogenic response (pre-existing ADA, treatment emergent ADA) after multiple intravitreal doses

Criteria for Pharmacodynamics:	
Further criteria of interest:
 
SRD part:
 

Systemic free Vascular Endothelial Growth Factor (VEGF) and free/total ANG2 levels after a single intravitreal dose

 
MRD part:
 

Change from baseline in CSFT in the study eye at Week 12 (Visit 5)

Changes from baseline in selected parameters derived from color fundus photography (CFP)/optical coherence tomography (OCT)/OCT-angiography (OCT-A) in both eyes

Systemic free VEGF and free angiopoietin 2 (ANG2) after multiple intravitreal doses

Safety criteria:	
Further criteria of interest:
 

Ocular inflammation in the study eye

Retinal haemorrhage in the study eye

BCVA reduction by more than 15 letters in the study eye

AEs including clinically relevant findings from the physical examination, safety laboratory tests, 12-lead electrocardiogram (ECG), vital signs

Statistical methods:	
Descriptive statistics will be provided for all endpoints for SRD and MRD parts. No statistical testing is planned.
 
In addition, in SRD part, the dose escalation will be guided by a Bayesian logistic regression model (BLRM) with overdose control that will be fitted to binary toxicity outcomes. The estimates of parameters will be updated as data are accumulated using the BLM.

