### **7.3.5 Pharmacokinetic and pharmacodynamic analyses**

The derivation of pharmacokinetic parameters is described in detail in the BI SOP [001-MCS-36-472](#). The determination of pharmacodynamic parameters AUEC,  $E_{max}$ ,  $E_{min}$  will follow the principles described for the respective PK parameters.

All evaluable patients who received at least one dose of BI 836880 will be included in the pharmacokinetic/ PD analysis. Patients who are considered as not evaluable will be listed with their individual sample concentrations and individual pharmacokinetic/ PD parameters, however, will not be included in descriptive statistics for sample concentrations, pharmacokinetic/ PD parameters or other statistical assessment.

Every effort will be made to include all concentration and response data in an analysis. If not possible, a case by case decision is required whether the value should only be excluded from half-life estimation or the complete analysis.

- If a concentration is only excluded from half-life determination, it will be used for all other calculations (e.g. descriptive statistics) and for graphical presentation.
- If a concentration value is excluded from all calculations, it will not be presented graphically or used for the calculation of descriptive statistics and parameter determination. However, the excluded concentration itself will be listed in the Clinical Trial Report (CTR) associated with an appropriate flag.

Concentrations will be used for graphs and calculations in the format that is reported in the bioanalytical report. Noncompartmental pharmacokinetic analyses of the sample concentration-time data will be performed using a validated software program, e.g. Phoenix WinNonlin. Only concentrations within the validated concentration range will be used for the calculation of pharmacokinetic parameters. For pre-dose samples, the actual sampling time will be set to zero.

Sample concentrations will be plotted graphically versus time for all evaluable subjects as listed in the drug concentration-time tables. For the presentation of the mean profiles, the geometric and arithmetic mean and the planned blood sampling times will be used. If the actual sampling time deviates significantly from the planned time, the corresponding sample concentration will be excluded from the calculation of descriptive statistics.

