6.6 HANDLING OF MISSING DATA AND OUTLIERS

Handling of missing data and outliers will be performed as described in CTP, Section 7.5.

The only exceptions where imputation might be necessary for safety evaluation are AE dates. Missing or incomplete AE dates are imputed according to BI standards (see BI-KMED-BDS-HTG-0035) (3).

Missing data and outliers of PK data are handled according to BI standards. PK parameters that cannot be reasonably calculated based on the available drug concentration-time data will not be imputed.

Section 7.5 of the CTP: *Missing baseline laboratory values will be imputed by the respective values from the screening visit.*

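### ADA and PD are summarised on the PK parameter set, so a treated patient with valid ADA or PD results but no evaluable PK endpoint drops out of those tables

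*SAP*

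**What the plan says.** SAP Section 6.4 defines the PKS as a subset of the treated set (TS): patients with at least one dose "who provide at least one PK endpoint that was not excluded due to a protocol deviation relevant to the evaluation of PK". An endpoint can also be excluded on a second ground ("or due to PK non-evaluability"). The threshold is low: "Thus, a subject will be included in the PKS, even if he contributes only one PK parameter value for one period". The sentence that states what the set is for names PK parameters only: "Descriptive and model-based analyses of PK parameters will be based on the PKS".

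Table 6.4: 1 then gives the row "PK, ADA and PD analysis" a mark in the PKS column and in no other. The same table puts safety parameters and the remaining secondary and further endpoints on the TS.

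ADA is a further criterion in the protocol synopsis, for example "Systemic immunogenic response (pre-existing ADA, treatment emergent ADA) after multiple intravitreal doses" in the MRD part. Protocol Section 7.3.5 limits the combined PK and PD analysis to evaluable patients and does not mention ADA. SAP Section 7 gives ADA its own report section (15.8), separate from PK (15.6) and PD (15.7).

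**The concern.** Whether a patient has a usable ADA or PD result is a different question from whether a usable PK endpoint can be derived. Table 6.4: 1 ties the first to the second. A valid ADA, VEGF or ANG2 result can then be missing from its summary table for a reason that has nothing to do with that result. The visible text gives no reason for the restriction, no second analysis set for ADA and no sensitivity analysis.

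At stake is the reported ADA frequency, pre-existing and treatment-emergent, in groups so small that one patient visibly moves the percentage.

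**Working it through.** The documents give no ADA rate, no PKS size and no exclusion rate, so there is no planned figure to reproduce. The check has two parts.

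**Can a treated patient have ADA or PD results but no PK endpoint?** Two routes follow from the documents.

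1. *Concentrations outside the assay range.* Protocol 7.3.5: "Only concentrations within the validated concentration range will be used for the calculation of pharmacokinetic parameters". SAP 6.6: "PK parameters that cannot be reasonably calculated based on the available drug concentration-time data will not be imputed". A patient whose post-dose concentrations are all out of range may yield no PK parameter, while the ADA and biomarker samples stay valid.
2. *Early departure from the MRD part.* In Protocol Table 10.1: 2 the pre-dose Day 1 visit includes PK, ADA and VEGF/ANG2 samples, and the next PK sample is at Day 29. A patient who leaves for good in between has a pre-dose ADA result, which is enough to classify pre-existing ADA, but no post-dose PK value. Treatment-emergent ADA cannot be assessed in that patient under any analysis set.

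**What would one lost patient do to the summary?** Group sizes are from SAP Section 6.1: 3 per SRD dose group (5 × 3 = 15), and 11, 4 and 12 in MRD cohorts 1, 2 and 3 (11 + 4 + 12 = 27). With x positives among n treated patients:

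- all treated: x/n
- k positives dropped: (x − k)/(n − k)
- k negatives dropped: x/(n − k)

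With x = 1 and k = 1, as an illustration:

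| Group | n | All treated | The only positive dropped | One negative dropped |
|---|---|---|---|---|
| SRD dose group | 3 | 1/3 = 33.3% | 0/2 = 0% | 1/2 = 50.0% |
| MRD cohort 2 | 4 | 1/4 = 25.0% | 0/3 = 0% | 1/3 = 33.3% |
| MRD cohort 1 | 11 | 1/11 = 9.1% | 0/10 = 0% | 1/10 = 10.0% |
| MRD cohort 3 | 12 | 1/12 = 8.3% | 0/11 = 0% | 1/11 = 9.1% |
| MRD total | 27 | 1/27 = 3.7% | 0/26 = 0% | 1/26 = 3.8% |

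With two positives in cohort 3 and one of them dropped, 2/12 = 16.7% becomes 1/11 = 9.1%. The shift can go either way. It is larger when a positive is lost, but nothing in the documents says which kind of patient would be lost.

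**The case against.** The strongest reply is that the rule will rarely bite.

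- One PK value admits a patient. Protocol Tables 10.1: 1 and 10.1: 2 schedule five post-dose PK samples in the SRD part and six in the MRD part, and every ADA time point is also a PK time point. A patient with a post-dose ADA result would need every relevant PK value to be unusable.
- On withdrawal of consent, Protocol 6.2.2.2 still asks for Visits 7 and 8. Both include PK sampling in the MRD part, which narrows the early-departure route.
- No deviation category in SAP Table 6.2: 1 excludes patients from the PKS specifically.
- The amendment history reports dose-proportional exposure in the SRD part, which suggests that PK parameters were obtained across the dose range, though not necessarily in every patient.
- The synopsis lists ADA under the pharmacokinetic criteria, so grouping it with PK is understandable. For PD, the protocol itself already imposes an evaluability condition.
- SAP Section 7 lists individual values of all patients, so an omitted patient remains visible there. Adverse events, including the ocular events of special interest, are analysed on the TS, and no hypothesis is tested.

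All of this stands, and it limits the size of the problem. It does not justify the rule, which brings no analytical benefit. Nor does the PD condition in Protocol 7.3.5 require a PK endpoint: it can be read as evaluable for PD.

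A reader might go further and infer that ADA itself causes the exclusion by lowering or masking measurable drug, so that the reported incidence is biased downward. The documents do not support that. They do not discuss any effect of ADA on BI 836880 concentrations or on the assay, and they do not define PK non-evaluability. The amendment history gives a geometric mean Cmax of 88.0 ng/mL at 2 mg, which scales to 88.0 × 0.06/2 = 2.6 ng/mL at 0.06 mg. That is an effect of dose, not of ADA, and without the assay limit it says nothing about how many patients would be lost.

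**Conclusion.** The point holds as a mismatch between the analysis set and the endpoint. As written, Table 6.4: 1 leaves treated patients with valid ADA or PD results out of the corresponding summaries when they have no evaluable PK endpoint. The text defining the PKS supports its use only for PK parameters.

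The severity is low. The number affected is unknown and may be zero. If no patient is excluded, the summaries are the same on either basis. If one is, the ADA percentage in a group of 3 to 12 can fall to 0% or rise, depending on that patient's status. No primary or secondary endpoint is involved, and the listings keep the data visible.

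Two limits apply. The table in the working assumes one positive and one lost patient per group, so it illustrates scale and does not estimate a bias. The detailed lists of further endpoints in both documents are not visible in the public versions, and they could affect how often the two sets differ.

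**What to change.** Split the combined row of SAP Table 6.4: 1 into three:

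- **PK parameters:** PKS, unchanged.
- **ADA:** treated patients with at least one ADA result for pre-existing ADA, and with at least one post-dose ADA result for treatment-emergent ADA.
- **PD:** treated patients with at least one evaluable PD value, whether or not PK is evaluable. This remains consistent with Protocol 7.3.5.

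State the denominators explicitly. SAP Section 7 bases percentages on everyone in the subject set, including patients with missing values, so simply moving the mark to the TS column would count patients without an ADA result in the denominator.

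The cost is one table row and a sentence on denominators. No new data are needed, and PK results do not change.
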